Appendix 5. Hepatic Monitoring Tests for Treatment-Emergent Abnormality

Selected tests may be obtained in the event of a treatment-emergent hepatic abnormality and may be required in follow-up with subjects in consultation with Chorus or its designee CRP.

Hepatic Monitoring Tests

Hepatic Hematology^a	Haptoglobin^a
Hemoglobin	
Hematocrit	Hepatic Coagulation^a
RBC	Prothrombin Time
WBC	Prothrombin Time, INR
Neutrophils, segmented	
Lymphocytes	Hepatic Serology^{ab}
Monocytes	Hepatitis A antibody, total
Eosinophils	Hepatitis A antibody, IgM
Basophils	Hepatitis B surface antigen
Platelets	Hepatitis B surface antibody
	Hepatitis B Core antibody
Hepatic Chemistry^a	Hepatitis C antibody
Total bilirubin	Hepatitis E antibody, IgG
Conjugated bilirubin	Hepatitis E antibody, IgM
Alkaline phosphatase	
ALT	Anti-nuclear antibody^a
AST	
GGT	Anti-smooth muscle antibody (or anti-actin antibody)^a
CPK	

Abbreviations: ALT = alanine aminotransferase; AST = aspartate aminotransferase; CPK = creatinine phosphokinase; GGT = gamma-glutamyl transferase; Ig = immunoglobulin; INR = international normalized ratio; RBC = red blood cells; WBC = white blood cells.

a Assayed by Chorus-designated local laboratory.

b Reflex/confirmation dependent on regulatory requirements and/or testing availability

| ANOVA | analysis of variance |
| ApoB | apolipoprotein |
| AST | alanine aminotransferase |
| AUC | area under the curve |
| BMI | body mass index |
| bpm | beats per minute |
| CI | confidence interval |
| Cmax | maximum concentration |
| CRP | clinical research physician |
| CRU | clinical research unit |
| CSR | clinical study report |
| DDI | drug-drug interaction |
| DGAT2 | Diacylglycerol acyltransferase 2 |
| ECG | Electrocardiogram |
| eCRF | electronic case report form |
| FFA | free fatty acid |
| HDL-c | high-density lipoprotein cholesterol |
| LDL-c | low-density lipoprotein cholesterol |
| Lp(a) | lipoprotein (a) |
| LY | LY3202328 |
| MAD | multiple ascending dose |
| MedDRA™ | Medical Dictionary for Regulatory Activities |
| mmHg | millimeters of mercury |
| MMRM | Mixed-effects model repeated measures |
| non-HDL-c | total cholesterol – high-density lipoprotein cholesterol |
| PCSK9 | proprotein convertase subtilisin/kexin type 9 |

| Abbreviation | Definition |
|------------------|---|
| PD | pharmacodynamic |
| PK | pharmacokinetic |
| PT | preferred term |
| QD | quaque die (once a day) |
| QT _{cf} | Fridericia corrected QT interval |
| SAD | single ascending dose |
| SAE | serious adverse event |
| SAP | Statistical analysis plan |
| SDTM | Study Data Tabulation Model |
| SOC | system organ class |
| TEAE | treatment emergent adverse event |
| TC | total cholesterol |
| TG | triglycerides |
| WHODD | World Health Organization Drug Dictionary |

1 INTRODUCTION AND OBJECTIVES

1.1 Introduction

The purpose of this statistical analysis plan (SAP) is to describe the analysis variables and statistical procedures that will be used to analyze and report the results from a Phase 1 study evaluating the safety and pharmacodynamics of LY3202328 (LY), a diacylglycerol acyltransferase 2 (DGAT2) inhibitor, in overweight, healthy subjects (Part A) and in dyslipidemic, statin-free, overweight, healthy subjects (Part B). This SAP addresses only the planned analyses based on amended Protocol I8Q-MC-GSEA(a) that was approved on 22 JUN 2016.

Changes to the protocol that impact the design, the data collected, or the statistical methods and that occur after the finalization of this SAP may require amendment of the approved SAP. Similarly, changes to the planned analysis variables and/or statistical methods described in the approved SAP may also require amendment of the SAP.

The formats for the tables, listings, and figures described in this SAP are provided in a companion documents. Changes to the formats of these reports that are decided after the finalization of the SAP will not require an amendment. In addition, any additional supportive or exploratory analyses requested after SAP approval will not require amendment of the SAP. These additional analyses will be described in the clinical study report (CSR).

Please see the study protocol for details about the study design, procedures, and schedule of assessments and see the electronic case report form (eCRF) for details about variables collected and their possible values.

1.2 Study Objectives

1.2.1 Primary Objective

The primary objective of this study is to explore safety and tolerability of single and multiple doses of LY in statin-free, overweight, healthy subjects.

1.2.2 Secondary Objectives

The secondary objectives of this study are:

- To assess the pharmacokinetic (PK) characteristics of LY in statin-free, overweight, healthy subjects after single and multiple doses.
- To evaluate the effect of food on the extent and rate of LY absorption.
- To determine the effects of LY upon multiple dose administration on:
 - Fasting lipid profiles
 - Simvastatin and atorvastatin exposure

1.2.3 Exploratory Objectives

The exploratory objective of this study is to explore the effects of LY on:

- Post-prandial lipid profiles.
- Fasting free fatty acids and β -hydroxybutyrate.
- Fasting apolipoprotein (Apo) B100, ApoC3, proprotein convertase subtilisin/kexin type 9 (PCSK9), lipoprotein (Lp [a]), and insulin.
- Body weight.

1.3 Study Design with Sample Size Justification

Study I8Q-MC-GSEA(a) (GSEA) is a first-in-man, Phase 1, randomized, double-blind, placebo-controlled, 2-part, ascending single- and multiple-oral dose study of LY in overweight, healthy subjects (Part A) and in dyslipidemic, statin-free, overweight, healthy subjects with a statin drug-drug interaction (DDI) assessments (Part B).

This study will be conducted in 2 parts: Part A, a single ascending dose (SAD) study design at a single site and Part B, a multiple ascending dose (MAD) study design conducted in multiple sites.

Eighteen statin-free, overweight, healthy males and female subjects may be enrolled in one of two 9-subject cohorts in Part A. Each subject is scheduled to receive 2 single doses of LY and 1 dose of placebo in ascending dose levels. This sample size is customary for Phase 1 studies evaluating safety, tolerability, and pharmacokinetic parameters, and is not powered on the basis of statistical hypothesis testing.

Forty statin-free, overweight, dyslipidemic subjects may be enrolled in Part B. Subjects will be enrolled in one of four dose-ascending 10-subject cohorts (8 subjects will receive LY and 2 subjects will receive placebo in each cohort). This sample size is a customary sample size for a Phase 1b MAD study evaluating safety, tolerability, and pharmacokinetic parameters.

2 General Statistical Methodology and Conventions

Chorus will designate a provider to generate the statistical analyses detailed in this SAP. All computations for statistical analyses will be performed using SAS® software, Version 9.3 or later. All SAS programs used in the production of statistical summary outputs will be validated with independent programming prior to finalization. In addition, all program outputs will be independently reviewed. The validation process will be used to confirm that all data manipulations and calculations were accurately done. Once validation is complete, a senior statistical reviewer will perform a final review of the documents to ensure the accuracy and consistency with this plan and consistency within tables. Upon completion of validation and quality review procedures, all documentation will be collected and filed by the project statistician or designee.

For the implementation of parametric methods of analysis, residual plots will be examined to determine if model assumptions are satisfied. Transformations or nonparametric methods of

analysis may be used if warranted. In some cases, nonparametric analysis may be the initially proposed method due to the expected distribution of response. Whenever alternative methods of analysis are required, the description of the new method along with the rationale for its use will be documented in the CSR.

The eCRF data for all subjects will be provided in Standard Data Tabulation Model (SDTM) datasets, and the production of the tables, figures and listings for the study will be generated from the SDTM datasets. Data listings supplied as part of the CSR will be sorted by investigative site and subject identification number, and subjects will be identified in the listings by the investigator number concatenated with the subject number.

2.1 Randomization Schedule and Unblinding Plan

Both Parts A and B are double-blinded so the subjects, investigator, and study site personnel will be blinded to treatment assignment – LY or Placebo. Simvastatin and atorvastatin dosing in Part B will also be determined by random assignment, but the subjects, investigators, and study site personnel will be unblinded to the statin assignment since commercially available product will be used. PRA Health Sciences International will be responsible for generating the schedules for both parts of the study.

In Part A, the subjects in each of the 9-patient cohorts -- Cohort 1 (1mg, 10mg, 100mg) and Cohort 2 (3mg, 30mg, 300mg) – will be randomized in a 1:1:1 ratio to one of the treatment sequences (Placebo, LY, LY), (LY, Placebo, LY), or (LY, LY, Placebo). The 30 mg dose level treatment assignments for Cohort 2 will be repeated in Period 4 to evaluate food effects on exposure. One of the period's treatment assignments for Cohort 1 will be repeated in Period 4 to evaluate the 600 mg dose level, so a couple subjects in Cohort 1 may receive Placebo twice.

In Part B, the subjects in each of four planned 10-patient cohorts -- Cohort 3 (5mg QD), Cohort 4 (20mg QD), Cohort 5 (100mg QD), and Cohort 6 (300mg QD) -- will be randomized to receive LY with simvastatin assessment (4 subjects), LY with atorvastatin assessment (4 subjects), placebo with simvastatin assessment (1 subject), or placebo with atorvastatin assessment (1 subject).

PRA Health Sciences will provide emergency codes to the investigator and pharmacy. A code, which reveals the treatment for a specific study subject, may be opened during the study only if the subject's well-being requires knowledge of the subject's treatment assignment. The investigator has the sole responsibility for determining if unblinding of a subject's treatment assignment is warranted for medical management of an event. However, if the investigator decides that unblinding is warranted, the investigator should make every effort to contact the Chorus clinical research physician (CRP) prior to unblinding a study subject's treatment assignment unless this could delay emergency treatment of the subject. If a study subject's treatment assignment is unblinded for the investigator, Chorus must be notified immediately and the subject must be discontinued from the study, unless the investigator obtains specific approval from a Chorus CRP for the study participant to continue in the study. All cases of emergency unblinding, including who and why, will be documented in the CSR.

To preserve the blinding of the study, only a minimum number of Chorus personnel will have access to the actual treatment assignments for a cohort before the dosing is completed for all patients in the cohort. The Chorus personnel with access to unblinded treatment information prior to the completion of dosing for a cohort will be limited to the Clinical Trial Supply Planner and potentially personnel monitoring ongoing safety of subjects in the study. All Chorus personnel can be unblinded to the actual treatment assignments for a cohort once dosing has been completed for the cohort. However, the blind for investigators, subjects and study personnel with direct contact with the sites will remain until the completion of the study.

After the last subject completes the study and all data management data activities have been completed – data entered, coding completed, and all queries resolved – the Chorus Asset Manager or designee will approve PRA Health Sciences to release the randomization schedule to the reporting team.

Upon completion of the study, all codes must be returned to Chorus or its designee.

2.2 Analysis Populations and Treatment Groups

The study population will consist of 18 statin-free, overweight, healthy male and female subjects in Part A and 40 statin-free, overweight, healthy male and female subjects with dyslipidemia in Part B, aged 18 to 70 years old inclusive for males, or 40 to 70 years old, inclusive for females. The number of subjects in the study population may increase if replacement subjects are treated in the study.

2.2.1 Analysis Populations

Two analysis populations will be used in this study:

- Safety data and baseline information will be analyzed using the **Safety Population**. The Safety Population is defined as all randomized subjects who received at least one dose of study treatment.
- Pharmacodynamics (PD) data will be analyzed using the **PD Population**. The PD Population is defined as all subjects who received at least one dose of LY and have both a baseline and post-baseline assessment of at least one PD parameter.

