2.2.2 Treatment Groups

During Part A, subjects will be treated in multiple dosing periods with single doses of a subset of the treatments -- Placebo, and 1mg, 3mg, 10mg, 30mg, 100mg, 300mg, or 600mg of LY. Dosing will be performed in a fasted state, except in the fourth dosing period for Cohort 2 when subjects will be dosed with 30mg LY after a standard meal. The treatment groups for Part A will be the dose levels of LY, plus the group 30mg LY fed.

During Part B, subjects will be enrolled in one of four dose-ascending groups (5mg LY, 20mg LY, 100mg LY, and 300mg LY) where they will be randomized to receive LY or placebo. The treatment groups for Part B will be Placebo, 5mg LY, 20mg LY, 100mg LY, and 300mg LY.

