All PD analyses will be performed using the PD population. Presentations of PD analyses will include the number of subjects with data at each time point plus related statistics derived from the analysis. Subjects who received Placebo during more than 1 dosing period in Part A will have their data from different dosing periods reported separately. The following sections contain the planned analyses. If plots of the raw data or residuals suggest alternative analysis techniques, such as log-transformation or nonparametric methods, then additional analyses will also be performed. The rationale for and results of the alternatives techniques will be described in the CSR.

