6.1.2 Fasting Lipid Profile Analyses in Part B

Fasting lipid profiles will be collected from all subjects in Part B just prior to dosing on the day of dosing, Day 7, Day 14, Day 21, and Day 28, and 7 (Day 35) days after stopping dosing of the randomized treatment. An additional follow-up assessment will be collected 14 (Day42) or 28 (Day 56) days after stopping dosing of the randomized treatment for Cohort 3 (5mg QD) and Cohorts 4 through 6, respectively.

A last on-treatment observation measurement will be derived for each subject using the last post-dose measurement for a lipid parameter taken while the subject is taking study medication during the 28-day treatment period. Change from baseline for each of the lipid parameters will be derived for each of the post-dosing time points (Days 7, 14, 21, 28, 35, and 42 or 56) and the last on-treatment observation using the pre-dose measurement from the first day of dosing as the baseline.

Descriptive statistics for the measurement at baseline and the measurement and change from baseline at each post-baseline time point plus the last observation will be tabulated.

An MMRM analysis will be conducted for each lipid parameter using the change from baseline values from Days 7, 14, 21, 28, 35, and 42. The MMRM model for change from baseline will contain fixed effects for treatment, time, and their interaction, a random effect for subject, and the baseline measurement as a covariate. Since the time points are evenly spaced the covariance structure among the repeated measurements for a subject will be assumed to be common across subjects and modeled using a autoregressive(1) 7x7 matrix. Satterthwaite's approximation will be used to estimate denominator degrees of freedom. Any missing assessments will be assumed to be missing at random, so estimates of treatment effects from the model will be unbiased.

These analyses will be performed using the SAS procedure PROC MIXED. The tabular output for these MMRM analyses will present the least squares means, standard errors and 95% confidence intervals and Type 3 p-values for each main effect marginal. Pairwise contrasts of the least squares means between the LY dose levels and placebo along with the associated 95% confidence interval and Type 3 p-values will also be provided at each time point using LSMESTIMATE statements.

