6.2.2 Post-prandial Lipid Profile Analyses in Part B

Measurement of the lipids TC, TG, HDL-c, LDL-c, and non-HDL-c will be obtained just prior to the midday meal on Days -1 and 28 of dosing. Post-meal measurements will be collected on both days at 0.5, 1, 2, and 4 hours after the meal for all subjects in Part B.

Change from baseline for each of the lipid parameters will be derived for each of the post-meal time points using the pre-meal measurement as the baseline, and the level of excursion within the 4-hour post-meal period will be determined using the post-meal AUC, as described in Section 6.2.1.

Descriptive statistics for the post-meal AUC at Days -1 and 28 as well as the difference between Days -1 and 28 will be presented by treatment group.

An ANCOVA will be conducted for each lipid parameter using the difference in post-meal AUC values from Day -1 to Day 28. The ANCOVA model will have a fixed effect for treatment, a random effect for subject, and the Day -1 post-meal AUC as a covariate.

Boxplots of the lipid values at pre-meal and each planned post-meal time point (0.5, 1, 2, and 4 hours post-meal) will be presented for each treatment group for both Day -1 and Day 28.

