6.3 Exploratory Biomarkers

The exploratory biomarkers FFA, β -hydroxybutyrate, and ApoB100 will be assessed from samples collected from all subjects in Part B on Day -1, Day 7, Day 14, Day 21, and Day 28,

plus 7 (Day 35) and 14 (Day 42) or 28 (Day 56) days after stopping dosing of the randomized treatment, while the biomarkers ApoC3, PCSK9, Lp(a) and insulin will only be collected on Day -1, Day 14, Day 28, Day 35, and Day 42 or 56. While the subjects are receiving randomized study medication samples will be collected just prior to dosing.

For each parameter a last on-treatment observation measurement will be derived for each subject using the last post-dose measurement for a parameter taken while the subject is taking study medication during the 28-day treatment period. Change from baseline for each parameter will be derived for each of the post-dosing time points (Days 7, 14, 21, 28, 35, and 42 or 56) and the last on-treatment observation using the Day -1 measurement as the baseline.

Descriptive statistics for the measurement at baseline and the measurement and change from baseline at each post-baseline time point plus the last observation will be tabulated.

An MMRM analysis will be conducted for each parameter using the change from baseline values. The MMRM model for change from baseline will contain fixed effects for treatment, time, and their interaction, a random effect for subject, and the baseline measurement as a covariate. Since the time points are evenly spaced the covariance structure among the repeated measurements for a subject will be assumed to be common across subjects and modeled using an autoregressive matrix. The analyses will be conducted and tabulated as described in Section 6.1.2.

Plots of the least squares mean \pm standard error estimates for each parameter over time (baseline through Day 56) will be provided by treatment group.

A last on-treatment observation analysis will be performed for change from baseline using an ANCOVA model with a fixed effect for treatment, a random effect for subject and the baseline value as a covariate. The analyses will be conducted and tabulated as described in Section 6.1.2.

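### The SAP's PD Population admits only subjects dosed with LY, which removes the whole Part B placebo group from the lipid and biomarker comparisons that need it

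*SAP*

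**What the plan says.** SAP 1.1 defines LY as LY3202328, the active drug. SAP 2.2.1 then sets two populations. The Safety Population takes any randomized subject given study treatment, so placebo counts. The PD rule is narrower: "The PD Population is defined as all subjects who received at least one dose of LY", with baseline and post-baseline data on at least one PD parameter also required. The opening of SAP section 6 leaves no exception: "All PD analyses will be performed using the PD population".

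Other parts of the SAP assume that placebo subjects are in the PD data:

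- SAP 2.1 gives the placebo allocation in each Part B cohort: "placebo with simvastatin assessment (1 subject), or placebo with atorvastatin assessment (1 subject").
- SAP 2.2.2: "The treatment groups for Part B will be Placebo, 5mg LY, 20mg LY, 100mg LY, and 300mg LY".
- SAP 3.1 reports PD Population counts by treatment group.
- SAP 6.1.2 specifies, for the MMRM: "Pairwise contrasts of the least squares means between the LY dose levels and placebo". It asks for the same comparison in the last on-treatment ANCOVA.
- SAP 6.3 carries this over to the exploratory biomarkers: "The analyses will be conducted and tabulated as described in Section 6.1.2".
- SAP 6.2.2, for the post-prandial AUC: "The ANCOVA model will have a fixed effect for treatment, a random effect for subject". It names no pairwise contrasts.

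**The concern.** Part B does not cross subjects over. A subject randomized to placebo stays on placebo through Day 29 and can never meet a rule that requires a dose of LY. The population definition therefore deletes the control group that the analysis sections rely on.

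The effect of multiple dosing on fasting lipids is a secondary objective, and Part B is the only multiple-dose part. Without placebo, what remains is change from baseline within each dose and comparisons between LY doses. No placebo-controlled estimate can be made, so changes common to all subjects (diet during confinement, the single statin dose on Day -7, time on study) have no control to be judged against.

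Timing is a secondary issue. SAP 2.1 says: "All Chorus personnel can be unblinded to the actual treatment assignments for a cohort once dosing has been completed for the cohort". Protocol 11.3.4 also has unblinded sponsor staff reviewing triglycerides, LDL-c, non-HDL-c and ApoB100 after the 20, 100 and 300 mg levels. A population definition corrected late would be corrected after some sponsor staff had seen these endpoints by treatment.

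**Working it through.** **1. Planned numbers.** Inputs: 4 cohorts of 10, two statin strata of 5, and 4:1 allocation within stratum (protocol 6.1.2, SAP 2.1).

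- LY: 4 cohorts × 2 strata × 4 = 32.
- Placebo: 4 × 2 × 1 = 8.
- Total: 32 + 8 = 40, which reproduces the protocol's planned Part B enrolment.

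**2. Applying the PD rule.** At most 32 subjects qualify, all on LY, and 0 of 8 placebo subjects do. Share excluded: 8/40 = 20%. Any replacement placebo subject would be excluded too.

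**3. Estimability.** Take a design matrix with one column for each Part B treatment group (Placebo, 5, 20, 100, 300 mg).

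| PD rule | N | Rank (5 columns) | LY − placebo contrasts estimable |
|---|---|---|---|
| As written | 32 | 4 | 0 of 4 |
| LY or placebo | 40 | 5 | 4 of 4 |

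**4. How many planned results are affected.** Only days shared by all cohorts are counted. The last follow-up visit (Day 42 or 56) differs by cohort and is left out, although SAP 6.1.2 lists Day 42 in the MMRM.

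- Fasting lipids (TG, TC, HDL-c, LDL-c, non-HDL-c). MMRM: 5 lipids × 4 doses × 5 days (7, 14, 21, 28, 35) = 100. Last on-treatment ANCOVA: 5 × 4 = 20. Total: 120.
- FFA, β-hydroxybutyrate and ApoB100, MMRM: 3 × 4 × 5 days = 60.
- ApoC3, PCSK9, Lp(a) and insulin, MMRM: 4 × 4 × 3 days (14, 28, 35) = 48.
- Biomarker last on-treatment ANCOVA: 7 × 4 = 28. Biomarker total: 60 + 48 + 28 = 136.
- Post-prandial ANCOVA: the treatment effect falls from 5 levels to 4, so its numerator degrees of freedom fall from 4 to 3.

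**5. Precision once placebo is restored.** Each contrast is 8 versus 8, with placebo pooled over cohorts.

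- SE = SD × √(1/8 + 1/8) = 0.50 SD.
- Single-time ANCOVA: df = 40 − 5 group means − 1 covariate = 34, t = 2.032, so the 95% half-width = 2.032 × 0.50 = 1.02 residual SD.

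This assumes full retention and no loss from baseline imbalance.

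**6. Part A.** Each of the three sequences holds two LY doses and one placebo dose (SAP 1.3 and 2.1). All 2 cohorts × 9 subjects × 1 = 18 fasted placebo dosings in Periods 1 to 3 therefore stay in if everyone completes. The 2 × 3 = 6 subjects who start on placebo would be lost only if they left before their first LY dose. A replacement subject who received only placebo would also be lost.

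**The case against.** The strongest reply is that this is an obvious drafting slip. The treatment-group list, the PD counts by group and the ordered contrasts all show that placebo was meant to be included. The error is also conspicuous: a literal run produces no placebo estimate, so it cannot quietly bias a result. The objective is secondary, the trial is not powered for hypothesis testing, and the SAP's safety tables already include placebo. All of that stands. It explains how the error arose, but it does not reconcile the text: a programmer must either depart from the SAP's population or leave out its contrasts.

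Several narrower objections have force:

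- **Late correction.** Restoring a randomized arm involves no outcome-dependent choice of subjects, and SAP 2.1 releases the randomization schedule to the reporting team only after the last subject finishes and queries are resolved. The risk of a data-driven change is small. Early correction is mainly tidier.
- **Dose comparisons.** Comparisons across 5 to 300 mg would give some separation of drug effect from shared change, though across cohorts that are not concurrent. What is lost is the placebo-controlled estimate.
- **600 mg.** Protocol 11.1 describes a possible separate cohort, which could include placebo-only subjects. SAP 2.1 instead gives 600 mg to Cohort 1 in Period 4, and subjects who completed Periods 1 to 3 would already have received LY.
- **Contrast counts.** The 120 and 136 repeat one fact, 8 versus 0, over analytes and days. They show reach, not separate errors.
- **Protocol 11.3.** Its assignment of PK/PD analyses to the PK population may refer to exposure-response work, which SAP section 9 sends to a separate SAP. On either reading, the protocol supplies no PD population containing Part B placebo subjects, since protocol 11.2 restricts both of its populations to LY recipients.

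**Conclusion.** The definition is wrong as written and must be corrected. It excludes 8 of 40 planned Part B subjects, which is the entire control group, and makes every Part B LY-versus-placebo contrast for fasting lipids and exploratory biomarkers inestimable. The post-prandial ANCOVA loses its placebo level. This rests on the planned allocation, on LY meaning the active drug as SAP 1.1 defines it, and on there being no exception elsewhere in the SAP; the companion table formats were not available. Part A is essentially unaffected, and so are the SAP's safety analyses. A PK population limited to LY recipients is not itself a fault.

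**What to change.** **SAP 2.2.1.** Define the PD Population as all randomized subjects given one or more doses of study treatment, whether LY or placebo, and keep the existing baseline and post-baseline condition. This one sentence removes the contradiction.

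**Protocol, for alignment.**

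- In 11.2, extend the Safety population to recipients of LY3202328 or placebo. That matches the SAP and the primary endpoint in 11.3.1.2, which covers events after either.
- In 11.2, add the same PD population and change the number of populations from two to three.
- In 11.3, state that PK, PD and safety analyses use the PK, PD and Safety populations respectively. The PK population can stay limited to LY recipients.

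**Timing.** Make the SAP change before the sponsor is unblinded to any Part B cohort. If that point has passed, record in the CSR when and why the change was made.

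**Cost.** One SAP sentence and three short protocol edits, with no new data, visits or subjects. The protocol edits need the usual amendment process; the SAP correction need not wait for them.
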